MRD	minimal residual disease		
NHL	Non-Hodgkins lymphoma		
PBMCs	peripheral blood mononuclear cells		

Abbreviation	Definition
PCI-32765	oral formulation of PCI-32765 (study drug) provided in hard gelatin capsules also known as "PCI-32765 PO Hard Gelatin Capsule"
PD	progressive disease
PE	physical examination
PET	positron emission tomography
P-gp	permeability glycoprotein
PR	partial remission (response)
QTc	corrected QT interval
SAE	serious adverse event
SD	stable disease
SLL	small lymphocytic lymphoma
SOC	standard of care
SPD	sum of the product of the diameters
TLS	tumor lysis syndrome
ULN	upper limit of normal
WM	Waldenström's macroglobulinemia
XLA	X-linked agammaglobulinemia

STUDY SYNOPSIS

Title:	A Long-term Safety Study of Bruton's Tyrosine Kinase (Btk) Inhibitor PCI-32765 in B Cell Lymphoma and Chronic Lymphocytic Leukemia		
Protocol number:	PCYC-1103-CA		
Phase:	Not applicable		
Indication:	B cell lymphoma and chronic lymphocytic leukemia (CLL)		
Study drug and comparator:	PCI-32765 PO Hard Gelatin Capsule (referred to as PCI-32765) No comparator is used in this study.		
Objectives:	The primary objective is to determine the long-term (> 6 months) safety and tolerability of a fixed daily dosing regimen of PCI-32765.		
Study design:	This is an open-label, monotherapy, multicenter, extension study open to subjects meeting requirements for roll over from their parent protocol and want to continue receiving study drug. Subjects from PCYC-04753 who had disease progression may enroll in this study at a higher dose level of PCI-32765 (not to exceed 840 mg/day) than dose level in PCYC-04753 study. Subjects enrolled in this study will receive once daily dosing with PCI-32765 at the same dose level they were receiving in the parent study. One cycle is 28 days. Treatment may be continued as long as there is no evidence of progressive disease or unacceptable toxicity. Safety and efficacy assessments will be performed at a minimum of every 3 cycles. At each visit, adverse events (AEs) of Grade 3 or 4 in severity, which are either new or represent detectable exacerbations of pre-existing conditions, events of special interest and ongoing AEs from parent protocol will be recorded. All serious adverse events (SAEs) must be recorded. Efficacy assessments will be performed in accordance with the Guidelines for the Diagnosis and Treatment of CLL ⁹ (Appendix 4), International Working Group Revised Response Criteria for Malignant Lymphoma ¹⁰ (Appendix 5), and Waldenström's Macroglobulinemia (WM) ¹¹ (Appendix 6). If signs and symptoms provide evidence of progressive disease (PD), PD must be confirmed by CT. Upon discontinuation of study treatment, a Safety Follow-up Visit (SFU) will be performed prior to the start of a new anticancer		
	therapy or approximately 30 (± 7) days after the last dose of study drug, whichever occurs first. If a subject discontinues treatment for reasons other than disease progression, response assessments will be continued approximately every 3 cycles until disease progression.		
	Once a subject has progressive disease, collect subsequent anticancer therapy and subject survival status approximately once every 3 months. At a visit when it is determined that a subject has		

	progressed, collect blood samples for pharmacodynamics and pharmacokinetics analyses (e.g., Btk occupancy and B cell activation) (refer to Section 6.1.)		
Major inclusion/exclusion criteria:	For the complete list of inclusion/exclusion criteria refer to Section 4.0.		
	Major Inclusion Criteria:		
	1. Men and women with recurrent surface immunoglobulin positive B cell non-Hodgkin's lymphoma (NHL) according to WHO classification, (including, but not limited to, CLL/small lymphocytic lymphoma [SLL], Waldenström's macroglobulinemia [WM], mantle cell lymphoma [MCL], and diffuse large B cell lymphoma [DLBCL]) who have met requirements for roll over from their parent protocol and want to continue study drug.		
	2. Female subjects of childbearing potential must have a negative serum or urine pregnancy test within 3 days of the first dose of study drug and agree to use dual methods of contraception during the study and for 90 days following the last dose with study drug. Post menopausal females (>45 years old and without menses for >1 year) and surgically sterilized females are exempt from this criterion.		
	3. Male subjects must use an effective barrier method of contraception during the study and for 3 months following the last dose if sexually active with a female of childbearing potential.		
	4. Willing and able to participate in all required evaluations and procedures in this study protocol including swallowing capsules without difficulty.		
	5. Ability to understand the purpose and risks of the study and provide signed and dated informed consent and authorization to use protected health information (in accordance with national and local patient privacy regulations).		
	Major Exclusion Criteria:		
	1. A life-threatening illness, medical condition or organ system dysfunction which, in the investigator's opinion, could compromise the subject's safety, interfere with the absorption or metabolism of PCI-32765, or put the study outcomes at undue risk.		
	2. Lactating or pregnant.		
Endpoints:	The primary endpoint of this study is the frequency, severity, and relatedness of AEs.		
	Other endpoints of this study are:		
	Long-term tolerability as measured by treatment-related SAEs and discontinuation of study treatment due to AEs.		
	PD and death events		
	Documented responses		

Safaty plans	This study will be monitored in accordance with the arrange?		
Safety plan:	This study will be monitored in accordance with the sponsor's Pharmacovigilance Committee procedures. Adverse events and serious adverse events (SAEs) will be reviewed internally on an ongoing basis to identify safety concerns.		
Study treatment:	PCI-32765 will be administered orally once daily at the same dose level of PCI-32765 as they received in the parent PCI-32765 study. Subject from PCYC-04753 who had disease progression may enroll in this study at a higher dose level of PCI-32765 (not to exceed 840 mg/day) than dose level in PCYC-04753 study. One cycle is 28 days.		
Concomitant therapy and clinical practice:	Concomitant medications which are permitted while on study treatment are provided in Section 5.5.1.		
	Any chemotherapy (e.g., chlorambucil, bendamustine, cyclophosphamide, pentostatin, or fludarabine), anticancer immunotherapy (e.g., rituximab, alemtuzumab, or ofatumumab), experimental therapy, or radiotherapy are prohibited during the Treatment Phase. Localized, hormonal, or bone sparing treatment for non-B-cell malignancies may be considered with approval of the medical monitor. Localized radiotherapy for medical conditions other than the underlying B-cell malignancies are allowed after consultation and approval by the medical monitor. Corticosteroids at dosages equivalent to prednisone >20mg/day administered consecutively for 14 days or longer are prohibited. For medications to be used with caution refer to Section 5.6.		
Statistical methods:	No formal statistical tests of hypotheses will be performed as this is an open-label, long-term, follow-up study. This study will remain open as long as there are active studies of PCI-32765 with subjects who could be eligible for this protocol.		
	Demographic characteristics, laboratory parameters, concomitant therapy, and AE incidence rates will be summarized using descriptive statistics. All subjects who receive at least 1 dose of study drug will be included in the safety and efficacy analyses.		
	All available efficacy and safety data will be included in data listings and tabulations. No imputation of values for missing data will be performed. Subjects lost to follow-up will be included in statistical analyses to the point of their last evaluation. All study data will be examined using standard data management operating procedures.		

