6.1 DESCRIPTION OF PROCEDURES

Informed Consent

Screening

The subject must read, understand and sign the IRB-approved informed consent form (ICF) confirming his or her willingness to participate in this study before initiating any screening activity that is not standard of care. Subjects must also grant permission to use protected health information.

Medical History

Screening

Medical history, concomitant medications, and any ongoing signs or symptoms from the prior PCI-32765 protocol must be recorded in the site's source documentation.

Adverse Events

At all visits (except Post-treatment and Post-PD follow up assessments)

The accepted regulatory definition for an AE is provided in Section 7.1. Adverse events that meet the criteria for SAEs, events of special interest (Section 7.2.4), and AEs of grade 3 or higher in severity will be recorded from the subject's first dose of study drug until 30 days after study drug discontinuation or start of a new anticancer therapy. Important additional requirements for reporting SAEs are explained in Section 7.2.

Concomitant Medication Use

At screening visit and during study when associated with protocol specified AE or SAE. Verify concomitant medication use to ensure subjects' eligibility to remain on study and when associated with a protocol specified AE/SAE. See Section 7.0 for further AE/SAE details.

Confirmation of Eligibility

Screening

Perform all necessary procedures and evaluations to document that the subject meets each eligibility criterion. Screening evaluations must be completed within 14 days before the subject's first dose of PCI-32765 under this protocol.

Physical Examination and Vital Signs

At all visits (except Post treatment and Post PD follow up assessments)

The screening physical examination will include, at a minimum, the general appearance of the subject, height (screening only) and weight, and examination of the skin, eyes, ears, nose, throat, lungs, heart, abdomen, extremities, musculoskeletal system, nervous system, and lymphatic system.

Symptom-directed physical exams will be done during the treatment period and at the Safety Follow-up Visit.

Vital signs will include blood pressure, pulse, respiratory rate, and body temperature. Vital signs and weight will be measured at every visit. Screening vital signs and weight do not need to be repeated if performed on prior PCI-32765 protocol within 14 days before the first administration of study drug on this protocol.

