6.3.1 Safety Follow-up Visit

The Safety Follow-up Visit will be conducted prior to the start of a new anticancer treatment or 30 (±7) days after the last PCI-32765 dose, whichever occurs first, to monitor for ongoing AEs (refer to Section 7.0) and to document the occurrence of any new AEs. The Schedule of Assessments (Appendix 3) describes the procedures required for the Safety Follow-up Visits.

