7.2.1 Adverse Event Reporting Period

The AE reporting period for this study begins when the subject takes the first dose of study drug and ends 30 days after the last dose of study drug. Ongoing AEs from parent protocol must be followed to resolution or until the investigator assesses the subject as stable, or the subject is lost to follow-up or withdraws consent. SAEs occurring after 30 days following the last dose of study drug should also be reported if considered related to study drug. If an SAE is present at the Safety Follow-up Visit, the SAE (and associated AEs and concomitant medications) should be followed to resolution or until the investigator assesses the subject as stable, or the subject is lost to follow-up or withdraws consent. Resolution/stable means the subject has returned to baseline state of health or the investigator does not expect any further improvement or worsening of the event.

If a death occurs within 30 days after the last dose of study drug the death must be reported to the Sponsor as an SAE.

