7.2.2 Assessment of Adverse Events

Investigators will assess the occurrence of AEs and SAEs at all subject evaluation time points during the study. All AEs and SAEs whether volunteered by the subject, discovered by study personnel during questioning, or detected through physical examination, clinically significant laboratory test, or other means will be recorded in the subject's medical record and on the AE eCRF and, when applicable, on a SAE Worksheet.

Each recorded AE or SAE will be described by its duration (i.e., start and end dates), severity, regulatory seriousness criteria, if applicable, suspected relationship to the investigational product (see following guidance), and any actions taken.

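### The Safety Follow-up Visit may fall up to 7 days before the AE reporting period ends, leaving days 24–30 with no scheduled AE assessment

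*Protocol*

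**What the plan says.** **Visit timing.** The synopsis (Study design) sets the Safety Follow-up Visit before the start of a new anticancer therapy or "approximately 30 (± 7) days after the last dose of study drug, whichever occurs first". Section 6.3.1 repeats this as "30 (±7) days after the last PCI-32765 dose, whichever occurs first, to monitor for ongoing AEs", and adds that new AEs are documented at this visit. Section 3.1 and Appendix 3 carry the same two-sided window.

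**AE reporting period.** Under Section 7.2.1 it starts with the first dose and "ends 30 days after the last dose of study drug". Section 7.1.1 uses the same 30 days.

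**Where AEs are assessed.** Section 6.1 gives the schedule as "At all visits (except Post-treatment and Post-PD follow up assessments"). Appendix 3 agrees: the Adverse events row is marked at screening, treatment and Safety Follow-up, and in neither of the two later columns. The hematology and serum chemistry rows also stop at the Safety Follow-up Visit. Section 7.2.2 is broader: "Investigators will assess the occurrence of AEs and SAEs at all subject evaluation time points during the study".

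**SAE follow-up.** Section 7.2.1: "If an SAE is present at the Safety Follow-up Visit, the SAE (and associated AEs and concomitant medications) should be followed to resolution", or until one of the other listed end points is reached.

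**Endpoint.** The only primary endpoint (Section 3.2) is the frequency, severity and relatedness of AEs.

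**The concern.** The Safety Follow-up Visit closes AE assessment after treatment, yet the lower side of its window lets it take place before the period it closes has ended. This needs no new anticancer therapy and no dispute over where the AE period ends; the minus 7 days is enough.

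Two things follow. First, ascertainment of AEs late in the post-dose period depends on the day for which a site books the visit. That includes Grade 3–4 laboratory abnormalities, which are found by testing. Secondly, the follow-to-resolution rule is anchored to the visit and not to the reporting period, so two SAEs with the same onset day can be handled differently because of booking alone. Missed events can only lower the counts, and the subjects concerned have just stopped drug, some of them for toxicity. Section 8.0 provides for no imputation of missing data, so the analysis would not restore what was not collected.

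**Working it through.** The protocol gives no sample size or power figure to reproduce. The check is day arithmetic, counting days from the last dose.

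**Inputs**
- Nominal visit day 30, tolerance ±7 (synopsis, 3.1, 6.3.1, Appendix 3).
- End of AE reporting period: day 30 (7.2.1).
- AE assessments scheduled after the Safety Follow-up Visit: none (6.1, Appendix 3).

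**Permitted window.** Earliest 30 − 7 = day 23; latest 30 + 7 = day 37.

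**Days of the AE period left after a visit on day s:** gap(s) = max(0, 30 − s).

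| Visit day s | 23 | 24 | 25 | 26 | 27 | 28 | 29 | 30–37 |
|---|---|---|---|---|---|---|---|---|
| Gap (days) | 7 | 6 | 5 | 4 | 3 | 2 | 1 | 0 |

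Only the early side of the window creates a gap.

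**Worst case as a share of the post-dose tail.** 7/30 = 23.3%.

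**Worst case as a share of the whole AE period.** The AE period covers treatment plus 30 days. The protocol gives no treatment duration for this study, so T is an assumption: share = 7/(T + 30).

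| Assumed T (days) | 28 | 84 | 182 | 365 | 730 |
|---|---|---|---|---|---|
| Share | 12.1% | 6.1% | 3.3% | 1.8% | 0.9% |

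**Average, as an illustration only.** Assume that visits fall evenly over days 23–37, among subjects who do not start new therapy first. Then 7 of 15 days (47%) precede day 30. The mean gap is (7 + 6 + 5 + 4 + 3 + 2 + 1)/15 = 28/15 = 1.87 days. That is 1.87/30 = 6.2% of the tail, 1.87/212 = 0.9% of the AE period when T = 182, and 1.87/395 = 0.5% when T = 365.

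**The SAE rule, case by case** (each SAE is taken to be still unresolved)

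| SAE onset | Visit day | In reporting period? | Present at visit? | Reached by the rule as written? |
|---|---|---|---|---|
| 20 | 23 | yes | yes | yes |
| 27 | 23 | yes | no | no |
| 27 | 31 | yes | yes | yes |
| 32, drug-related | 35 | no, but reportable under 7.2.1 | yes | yes |

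Rows 2 and 3 differ only in the visit date. Row 4 matters for the fix: a rule rewritten to cover only onset within the reporting period would drop it.

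**After the change.** With visits on days 30–37, gap(s) = 0 throughout, except where new anticancer therapy brings the visit forward.

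**The case against.** The strongest reply is that the duty to report does not stop at the visit, and that is correct. The AE period runs to day 30 whatever the visit date (7.1.1, 7.2.1). AEs ongoing at discontinuation are to be followed to day 30 (4.3). SAEs and their follow-up information are due within 24 hours of discovery, and the sponsor may ask for more (7.2.3). New malignancies are reported throughout follow-up (7.2.6). A reader might infer that a site may close AE collection on day 23. The documents do not support that: the gap is in scheduled ascertainment, not in the obligation.

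Section 7.2.2 also calls for AE assessment at every evaluation time point. This conflicts with the exception in Section 6.1, but it adds no visit tied to days 24–30. Subjects who stop without progression are seen again for disease assessments that include examination and a blood count, about every 3 cycles. Those contacts may bring an event to light later, but they are not timed to the end of the AE period.

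A reader might also infer that 30-day death counts are biased downward. That is not shown. A death within 30 days must be reported as an SAE (7.2.1). Survival status and cause of death are collected every 3 months after progression (6.3.3), subjects without progression are followed about every 3 months (6.3.2), and a subject who cannot be reached must be pursued (4.4). A death on day 27 would normally surface. Appendix 3 marks survival only in the post-progression column, but that does not establish a loss of deaths.

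Finally, 84 days separate the scheduled on-treatment AE visits, so the design already relies on recall over intervals much longer than 7 days, and there is no comparator or hypothesis test. This limits the importance of the point. It does not remove it: on-treatment recall is recovered at the next AE visit, whereas after the Safety Follow-up Visit there is none.

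**Conclusion.** The point holds in a limited form. The visit window permits the last scheduled AE assessment on day 23 while the AE period runs to day 30. Up to 7 days then have no scheduled AE or safety-laboratory ascertainment, and an SAE starting in them is not literally covered by the follow-to-resolution rule.

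The likely effect is a small under-ascertainment of post-treatment AEs and SAEs. The bound is 7 of 30 tail days; 23% should not be read as the share of primary-endpoint information at risk, because the AE period also includes all time on treatment (3.3% at an assumed 182 days, 1.8% at 365). These figures are days without a scheduled assessment, not events lost, and the protocol gives no basis for an event count. The averages rest on an assumed even spread of visits.

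The new-therapy branch is a separate matter. Section 6.1 records AEs "until 30 days after study drug discontinuation or start of a new anticancer therapy", whereas 7.2.1 has no cut-off at new therapy. Those passages need reconciling, but this finding does not depend on them.

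**What to change.** 1. In the synopsis, Section 3.1, Section 6.3.1 and Appendix 3, change 30 (±7) days to 30 (+7) days after the last dose. Keep the provision that brings the visit forward when a new anticancer therapy is about to start.
2. In Section 7.2.1, extend the follow-to-resolution rule and do not replace it. Leave the existing condition (SAE present at the visit) and add a second: *or has onset within the AE reporting period and is unresolved at its end*. Keeping the first condition means that a drug-related SAE starting after day 30 and found at a visit on, say, day 35 stays covered.

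The cost is wording in five places. Sites lose the option of booking this one visit early. No visit or test is added. The gap caused by the window falls from at most 7 days to 0.

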1.0 BACKGROUND INFORMATION

Note: for more detailed and comprehensive background information please refer to the PCI-32765 Investigator's Brochure (IB).

1.1 INVESTIGATIONAL PRODUCT NAME AND DESCRIPTION

PCI-32765 (ibrutinib) is a first-in-class, potent, orally administered covalently-binding inhibitor of Bruton's tyrosine kinase (BTK). Inhibition of BTK blocks downstream B-cell receptor (BCR) signaling pathways and thus prevents B-cell proliferation. In vitro, PCI-32765 inhibits purified BTK and selected members of the kinase family with 10-fold specificity compared with non-BTK kinases. PCI-32765 (IMBRUVICA®; ibrutinib) is approved by the U.S. Food and Drug Administration (FDA) for the treatment of: 1) mantle cell lymphoma (MCL) in patients who have received at least one prior therapy, 2) chronic lymphocytic leukemia (CLL) in patients who have received at least one prior therapy, 3) CLL in patients with 17p deletion, and 4) Waldenström's Macroglobulinemia. PCI-32765 is currently under investigation in various indications as a single agent and in combinations.

B cells are lymphocytes with multiple functions in the immune response, including antigen presentation, antibody production, and cytokine release. B cells express cell surface immunoglobulins comprising the B-cell receptor (BCR), which is activated by binding to antigen. Antigen binding induces receptor aggregation and the clustering and activation of multiple tyrosine kinases, which in turn activate further downstream signaling pathways. ¹⁸

The process of B-cell maturation, including immunoglobulin chain rearrangement and somatic mutation, is tightly regulated. It is thought that B-cell lymphomas and CLL result from mutations and translocations acquired during normal B-cell development. ¹⁹ Several lines of evidence suggest that signaling through the BCR is necessary to sustain the viability of B-cell malignancies.

The role of BTK in BCR signal transduction is demonstrated by the human genetic immunodeficiency disease X-linked agammaglobulinemia and the mouse genetic disease X-linked immunodeficiency, both caused by a mutation in the BTK gene. These genetic diseases are characterized by reduced BCR signaling and a failure to generate mature B cells. The BTK protein is expressed in most hematopoietic cells with the exception of T cells and natural killer cells, but the selective effect of BTK mutations suggests that its primary functional role is in antigen receptor signaling in B cells.¹

Data from Study PCYC-04753 demonstrate that although PCI-32765 is rapidly eliminated from the plasma after oral administration, once daily dosing with PCI-32765 is adequate to sustain maximal pharmacodynamic activity for 24 hours postdose at dose levels ≥2.5 mg/kg. In Study PCYC-04753, the BTK occupancies for the 2.5 mg/kg/day to 12.5 mg/kg/day cohorts and for the 560 mg continuous dosing cohort, were all above 90% at either 4 or 24 hours after drug administration.

For the most comprehensive nonclinical and clinical information regarding PCI-32765 background, safety, efficacy, and in vitro and in vivo preclinical activity and toxicology of PCI-32765, refer to the latest version of the PCI-32765 IB.

